8.4 Primary efficacy endpoint

The change in tumor cell proliferation as measured by Ki67 expression between baseline and the post-treatment tumor biopsy samples by central assessment.

The primary analysis will be done for the mITT analysis set. We only will analyse observed valid cases (observed-cases method).

The global null hypothesis is that the giredestrant (GDC-9545) does not differ from tamoxifen treatment group in the mean percentage of absolute difference in Ki67 between baseline score and after the treatment. The alternative hypothesis is that the giredestrant (GDC-9545) differs from the tamoxifen treatment group.

The test of the null hypothesis is based on a two-sided Wilcoxon unpaired test set at 0.05 alpha level. It includes treatment as a factor. The response variable is the absolute difference in Ki67 score after the treatment. We propose declaring the superiority of giredestrant (GDC-9545) therapy if shown to be superior in this analysis.

We will estimate the 95% confidence intervals (CI) for the mean and median of absolute difference between baseline and the post treatment evaluation in each study arm. The 95% confidence intervals (CI) for the mean and median difference between treatments are estimated by the T-Test and Hodges–Lehmann estimator, respectively.

Individual baseline and post-treatment Ki67 scores will be summarized with dot plots linking with a line the observations of the same patient. Absolute and relative change between baseline and post-treatment will be summarized with waterfall and bar plots.

8.5 Missing data imputation methods

The values of Ki67 could be missing for patients without valid analytic values or withdrawal. Missing values for primary endpoint will be managed with three methods:

- a) Observed case imputation: Only observed valid cases are analyzed.
- b) Last observation carried forward: Missing value are replaced by the last value observed before.
- c) The standard multiple imputation performed in three steps: (1) the imputation of non-monotone missing data using MCMC. A total of 10 complete datasets are generated within this step; (2) the imputation of monotone missing data with regression models; (3) the calculation of endpoint estimates, standard errors and p-values for each dataset; and (4) the combination of all dataset results by Rubin's rules.

8.6 Supportive analyses for primary efficacy endpoint

The primary endpoint analysis will be repeated for the PP and ITT set as described in the previous section. For ITT analysis the missing values for Ki67 after the treatment are imputed with baseline Ki67 scores based on the last observation carried forward principle (0 score in absolute difference of Ki67). For PP analysis only observed valid cases will be analysed.

Additionally, the following supportive analyses will be performed (**Table 6. Planned analyses for the primary endpoint.**):

- a) The Ki67 score after two weeks of treatment will be adjusted by baseline Ki67 scores. The analysis will be done for the mITT, ITT and PP analysis set (as appropriate). We only will analyse observed valid cases for mITT and PP analysis set. Alternatively, the missing management method for ITT analysis will be the multiple imputation.

The test of the null hypothesis is based on a linear regression model which includes treatment as a factor and baseline Ki67 score as covariate. The response variable is the Ki67 score after the treatment. Because of the non-asymptotic distribution of data, power transformations will be conducted with response and covariate. The transformed values of the Ki67 score are assumed to be a linear function of the treatment as:

$$Y = \beta_0 + \beta_1 X_1 + \beta_2 X_2$$

where

Y = The Ki67 score after the treatment,

β_0 denotes intercept,

β_1 denotes the treatment effect,

X_1 refers to the treatment groups (Giredestrant (GDC-9545) and tamoxifen),

β_2 denotes the Ki67 baseline score effect,

X₂ refers to the Ki67 baseline score.

The parameterization method is based on a reference group (tamoxifen). The p-values and 95% CI are estimated by the Wald method. The 95% CI will be also reported back transformed.

b) The relative percentage of change between baseline and the post treatment evaluation in each patient will be calculated using the baseline and post-treatment scores divided by baseline scores per 100. The 95% CI for the arithmetic and geometric mean in each arm will be estimated with T-Test.

The geometric mean will be estimated using the log values for the relative percentage of change. The log-transformation is designed for non-negative values, so we will add a constant to the individual values of relative percentage change before applying the transformation. The 95% CI for the geometric mean will be reported back transformed using the anti-log scale and subtracting the constant. The analysis will be done for the mITT, ITT and PP analysis set (as appropriate). We only will analyse observed valid cases for mITT and PP analysis set. Alternatively, the missing management method for ITT analysis will be the multiple imputation.

Table 6. Planned analyses for the primary endpoint.

ID	Set	Analysis sets	Main estimate and (Imputation Method)	Type of analysis
1	mITT	Patients excluded: -Central Ki67 < 10% or not evaluable at baseline. -<14 days of treatment. -Without the Ki67 central evaluation at baseline and after at most on the day after the completion of treatment.	Central Ki67 score Difference between baseline and post treatment evaluation. (Observed case)	Primary -Willcoxon unpaired -95% CI T-test -95% CI HL
2	ITT	All patients randomized regardless of IEs are included (Treatment policy strategy).	Central Ki67 score Difference between baseline and post treatment evaluation. (Last observation carried forward)	Supportive -Willcoxon unpaired -95% CI T-test -95% CI HL
3	PP	Patients excluded: -Central Ki67 < 10% or not evaluable at baseline. -Without the Ki67 central evaluation after the treatment -Patients with other major deviations in accordance steering committee.	Central Ki67 score Difference between baseline and post treatment evaluation. (Observed case)	Supportive -Willcoxon unpaired -95% CI T-test -95% CI HL
4	mITT	See above ID nr. 1	Central Ki67 score Ki67 score after the treatment adjusted by baseline score. -Box-cox transformation (Observed case)	Supportive -Linear regression (Wald test) adjusted by baseline scores
5	ITT	See above ID nr. 2	Central Ki67 score Ki67 score after the treatment adjusted by baseline score.	Supportive -Linear regression (Wald test) adjusted by baseline scores

ID	Set	Analysis sets	Main estimate and (Imputation Method)	Type of analysis
			-Box-cox transformation (Multiple imputation)	
6	PP	See above ID nr. 3	Central Ki67 score Ki67 score after the treatment adjusted by baseline score. -Box-cox transformation (Observed case)	Supportive -Linear regression (Wald test) adjusted by baseline scores
7	mITT	See above ID nr. 1	Central Ki67 score % of change between baseline and post treatment evaluation. (Observed case)	Supportive -95% CI for arithmetic and geometric means in each arm
8	ITT	See above ID nr. 2	Central Ki67 score % of change between baseline and post treatment evaluation. (Multiple imputation)	Supportive -95% CI for arithmetic and geometric means in each arm
9	PP	See above ID nr. 3	Central Ki67 score % of change between baseline and post treatment evaluation. (Observed case)	Supportive -95% CI for arithmetic and geometric means in each arm

CI: Confidence interval; HL: Hodges–Lehmann method; ITT: Intention to treat; mITT: Modified intention to treat; PP: Per protocol.

8.7 Secondary and subgroup analyses

The secondary efficacy endpoints will be done for the mITT analysis set. We only will analyse observed valid cases.

For quantitative measures (Ki67, ER, PR, and other molecular markers) the mean, median, geometric mean, standard deviation, interquartile range, and range will be reported as appropriate per study arm and visit. Summary statistics for the absolute and relative change between baseline and post-treatment will be also reported.

Individual baseline and post-treatment scores in quantitative measures will be summarized with dot plots linking with a line the observations of the same patient. Absolute and relative change between baseline and post-treatment will be summarized with waterfall and bar plots.

The difference between baseline and post-treatment evaluation will be compared in each arm with Wilcoxon paired test. We will estimate the 95% confidence intervals (CI) for the mean and median.

The difference between study arms at baseline and after the treatment will be compared with Wilcoxon unpaired test. We will estimate the 95% confidence intervals (CI) for the mean and median difference between treatments with T-Test and Hodges–Lehmann estimator, respectively. The comparison of quantitative score after two weeks of treatment in each arm will be adjusted by baseline scores based on linear regression. Power transformations will be deliberated.

For qualitative measures (CCCA [Ki67≤2.7%] after the treatment) we will calculate the number and proportion of patient achieving the cut-off criterion. We will estimate the proportions with the 95% Pearson-Clopper confidence intervals. The between arms comparison will be conducted with logistic regression models. Factor estimates, odds ratios, corresponding 95% confidence intervals, and p-value will be presented. P-values and 95% confidence intervals will be based on Wald test.

The comparison of primary and secondary endpoints between patient and molecular characteristics will be conducted if considered appropriate. The quantitative endpoints will be analyzed with linear regression based on Wald test. The binary endpoints will be analyzed with logistic regression models. Factor estimates, odds ratios, corresponding 95% confidence intervals, and p-value for applicable test statistics will be presented. P-values and 95% confidence intervals will be based on Wald test.

For all secondary analyses, we will use two-sided p-values with $\alpha \leq 0.05$ level of significance and 95% confidence intervals.

8.8 Safety analysis

Safety data will be analyzed in safety analysis sets. All safety measures will be described in each arm. We will summarize adverse events and adverse events of special interest, premature withdrawal from study medication, laboratory parameters, exposure to study medication, concomitant medications, vital signs, ECOG performance status, and physical examination.

The incidence of AEs and SAEs will be summarized according to the primary system-organ class (SOC) and within each SOC, by the Medical Dictionary for Regulatory Activities (MedDRA) preferred term. Additional summaries by frequency tables will also be provided for the AEs. Patients who died will be listed together with the cause of death.

Laboratory parameters, hematology and biochemistry, will be presented in shift tables of NCI-CTCAE grade at baseline versus worst grade during treatment.

Other safety variables, such as exposure to study medication, ECOG performance status, concomitant medications, vital signs, and physical examination, will be analyzed in a similar way. Frequency tables will summarize the exposure of study medication.

[REDACTED]

8.10 Interim analyses

No interim analyses are planned

8.11 Steering committee

A Steering Committee will be established for this study. It will be composed by the study site investigators, the Sponsor's Medical Monitor, the Scientific Global Coordinator, and additional physicians with experience in experimental therapy management.

Steering Committee meetings are scheduled to review the available safety of the first patient enrolled at each cohort who have completed treatment period, and every 6 months thereafter until communication of the study results. The Steering Committee will meet to review, discuss, and evaluate all the gathered feasibility, safety, and efficacy data. In case of any arising a concern, these meetings can also be called at any time at request of a participating investigator or the Sponsor study team. At these meetings, the Sponsor and the participating investigators must reach a consensus on feasibility, efficacy, and safety data. The Sponsor will prepare minutes from these meetings and circulate them to each investigator for comment prior to finalization.

Each study site investigator will monitor patient's data for serious toxicities on an ongoing basis.

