8.2 Sample size

The analysis will compare absolute changes for Ki67 expression between baseline score and the evaluation after the treatment. The sample size was based on a superiority contrast between two study arms analyzed with a two-sided t-test set at 0.05 alpha level. We assumed a 70% mean in giredestrant (GDC-9545) Arm vs. 50% mean in tamoxifen with a 29% common standard deviation, according to the results observed (Dowsett, Smith, et al., 2005). We planned 34 patients per arm to attain an 80% power.

The final analysis will be conducted with unpaired Wilcoxon test because of the non-asymptotic distribution of data. We assumed that asymptotic efficiency of Wilcoxon test relative to the t-test, never falls below 0.86 (Jr & Lehmann, 1956). In addition, we expect a 10% dropout rate. So, 46 patients per arm will be finally recruited. We used the R software version 4.0.2. released on 2020-06-22 ("pwr").

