3 ANALYSIS SETS

Modified intention to treat (mITT) set

All randomly assigned patients that accomplish major selection criteria (Central Ki67 $\geq 10\%$), with ≥ 14 days of treatment*, and the central Ki67 evaluated at baseline and at most on the day after the completion of treatment. Subjects will be analyzed according to treatment allocated. The mITT set will be used for primary and secondary efficacy analysis.

*One day of deviation from the 15 days of treatment indicated for the main objective will be accepted.

Intention-to-treat (ITT) analysis set

All patients randomized. Subjects will be analyzed according to treatment allocated. The ITT set will be used for supportive efficacy analyses.

Per protocol analysis (PP) set

All randomly assigned patients that accomplish major selection criteria, with Ki67 evaluable values at baseline and after the treatment, with a minimum exposure to the drugs assigned in the randomized arm, and without major protocol deviations. Criteria for determining the "per protocol" group assignment would be established by the Steering Committee before the statistical analysis begins. Subjects will be analyzed according to treatment received. The PP set will be used for supportive efficacy analyses. This analysis will only occur if this set differs by $\geq 10\%$ from the mITT set.

Safety analysis set

Includes all patients who received at least one dose of the study drug. Subjects will be analyzed according to treatment received. The safety set will be used for analyses of safety endpoints.

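### Protocol 8.11 lets a Steering Committee that includes enrolling investigators review accumulating efficacy data, not limited to pooled data, although no interim analysis is planned

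*Protocol*

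**What the plan says.** Protocol 8.11 sets up a Steering Committee made up of site investigators, the Scientific Global Coordinator, the sponsor's Medical Monitor and additional experienced physicians. It first meets on early safety, then every 6 months until the results have been communicated. Extra meetings can be called whenever a concern arises. Its task is to "review, discuss, and evaluate all the gathered feasibility, safety, and efficacy data", and the sponsor and participating investigators "must reach a consensus on feasibility, efficacy, and safety data".

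On interim looks, Protocol 8.10 says "No interim analyses are planned". SAP 5.1 agrees, and SAP 5.2 places the final analysis after database lock. Protocol 3.1 describes the trial as open-label. Neither document describes pooling, masking of Committee material or an independent monitoring committee.

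The efficacy claim rests on one test on the mITT set: "The test of the null hypothesis is based on a two-sided Wilcoxon unpaired test set at 0.05 alpha level" (Protocol 8.4, repeated in SAP 4.4.1).

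The Committee has one other statistical role. Protocol 8.3 and SAP 3 say that criteria for per-protocol "group assignment would be established by the Steering Committee before the statistical analysis begins". Protocol Table 6 and SAP Table 1 write out two of the per-protocol exclusions and leave other major deviations to the Committee. The set is supportive and is analysed only if it differs from mITT by at least 10%.

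**The concern.** The instruction in 8.11 and the denial in 8.10 do not fit together. A standing review of all efficacy data, with a duty to agree on it, is an interim look unless something restricts what is shown. Nothing does.

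The people in the room also run the trial:

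- Site investigators enrol patients and obtain the post-treatment tissue.
- The Medical Monitor verifies eligibility before inclusion (Protocol 6.1.2) and is consulted on samples with at least 350 but fewer than 500 viable cells (6.6.1). That second decision can bear on who has an evaluable central Ki67, and so on who enters the primary mITT set.
- The sponsor, the Scientific Global Coordinator and the site investigators are among those who approve protocol amendments (12.2).
- The sponsor may end the study at any time, on open-ended lists of reasons (3.3.4, 6.8).

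If these people know how Ki67 is running by arm, later enrolment, sample handling or amendments could be influenced by it. A reader of the final report could not rule that out. A lesser issue is that the same Committee completes the per-protocol criteria at a time not tied to database lock or to its knowledge of results.

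**Working it through.** **1. The plan's own figures.** Protocol 8.2 gives the inputs: "We assumed a 70% mean in giredestrant (GDC-9545) Arm vs. 50% mean in tamoxifen with a 29% common standard deviation", two-sided alpha 0.05, and "We planned 34 patients per arm to attain an 80% power".

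- Normal approximation: n = 2 × (1.960 + 0.842)² × 29² / 20² = 2 × 7.849 × 2.1025 = 33.0, rounded up to 34 per arm.
- Exact two-sample t: 33.99, so 34 per arm, with power 0.800.
- Wilcoxon allowance ("We assumed that asymptotic efficiency of Wilcoxon test relative to the t-test, never falls below 0.86"): 34 / 0.86 = 39.5, so 40.
- 10% dropout: 40 / 0.90 = 44.4, so 45 per arm, against 46 stated.

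The plan reproduces to within one patient per arm. It is a fixed-sample design with one primary test and no allowance for looks.

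**2. The provisions side by side.**

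| Question | What the documents give |
|---|---|
| Is efficacy reviewed at Committee meetings? | Yes, all gathered data (8.11) |
| Is the review limited to pooled or masked data? | No limit stated |
| Is it limited to after lock? | No; 6-monthly meetings run through accrual |
| Is an interim analysis planned? | No (8.10, SAP 5.1) |
| Is a test, boundary or early claim attached to a meeting? | No |
| Does 8.11 let the Committee stop the trial or recommend stopping? | No |

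The first three rows show what is permitted. The last three show why alpha is unchanged on the plan as written.

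**3. When data could exist.** The endpoint is read at about day 15, and accrual is about 16 months for 92 patients (8.1). Assume uniform accrual, meetings at about months 6 and 12, no dropout and no central-reading lag:

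- Month 6: 6/16 = 0.375 of the information, 92 × 0.375 = 34.5, about 34 patients.
- Month 12: 12/16 = 0.75, 92 × 0.75 = 69 patients.

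**4. Hypothetical worst case.** Suppose each look were tested at |Z| > 1.96 and a crossing led to a claim. Under the null, Z(t) = B(t)/√t with B a Brownian motion. Simulated with 2,000,000 replicates:

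| Looks (information) | Two-sided error | Error favouring giredestrant |
|---|---|---|
| 1 (the plan as written) | 0.050 | 0.025 |
| 0.375, 1 | 0.087 | 0.044 |
| 0.75, 1 | 0.073 | 0.037 |
| 0.375, 0.75, 1 | 0.104 | 0.052 |

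**5. Reach of the per-protocol criteria.** In Protocol Table 6 and SAP Table 1 the per-protocol set feeds analyses 3, 6 and 9, all supportive. The primary test is analysis 1, on mITT with written exclusions.

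**The case against.** The strongest reply is that 8.11 never mentions arms, Ki67, a comparison or a test. Some meetings fall after the final analysis, when efficacy review is proper. Read with 8.10 and SAP 5.1 and 5.2, the efficacy wording could mean only that. The documents also do not say when central post-treatment Ki67 is read or released, so by-arm results may not exist at a 6-monthly meeting. The listed termination reasons do not include efficacy, Protocol 12.1 speaks of safety or administrative grounds, and amendments also need ethics and authority approval.

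Much of this stands, and it rules out three stronger readings that a reader might infer:

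- *That the plan prescribes repeated by-arm looks at the primary outcome.* It permits them by setting no limit; it does not order them.
- *That the true type I error is about 10%.* That needs a claim rule at each look, and there is none. Nor is any extension or sample-size re-estimation provided for.
- *That the Committee sets per-protocol criteria after seeing results.* The text allows that order of events but does not state it, and the criteria cannot reach the primary test.

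The reply does not remove the conflict. The review covers all efficacy data gathered, starts during accrual, requires consensus, and takes place in an open-label trial with no masking provision. A reading lag would reduce what is available, but nothing says results are withheld until lock. SAP 4.1 accepts unadjusted multiple testing because the study is exploratory, but it does not address repeated looks, and Protocol 8.4 still proposes a superiority declaration at 0.05.

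**Conclusion.** The point holds as a conflict between 8.11 and the no-interim statements, with a risk of bias in conduct that the documents give no basis for quantifying. The stated two-sided alpha of 0.05 is unaffected on the plan as written.

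The figure of about 10% (0.104) marks only the outer edge of what acted-on looks could do. It rests on two looks, uniform accrual over 16 months, no reading lag and a claim at 0.05 each time. In the direction favouring giredestrant it is about 5.2%, against 2.5% for a single test. Meetings called ad hoc could add looks.

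The per-protocol part is minor: it touches supportive analyses 3, 6 and 9 only, and only if that set differs from mITT by at least 10%. The change is worth making because it costs so little, not because the primary test is broken.

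**What to change.** - **Protocol 8.11:** state that until database lock the Committee reviews safety and feasibility only, that any Ki67 shown is pooled over both arms, and that efficacy by arm is reviewed only after lock. Apply the efficacy part of the consensus sentence to post-lock meetings rather than deleting it.
- **Protocol 8.3 and SAP 3, with their analysis tables (minor):** write out the other-major-deviation criteria and date them, before lock and before any Committee member has access to post-treatment Ki67 by arm.

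The cost is wording: no extra patients, procedures or change in sample size. What is lost is a by-arm efficacy review during accrual, for which the plan states no decision use.

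If the sponsor does want by-arm looks that can lead to a decision, they should be declared as interim analyses with boundaries. For looks at 0.375, 0.75 and 1, O'Brien-Fleming-type nominal two-sided p-values of about 0.001, 0.020 and 0.043 hold the overall level at 0.05.

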9 ETHICAL CONSIDERATIONS

9.1 Regulatory and ethics compliance

The study will be performed and reported in accordance with the guidelines of the International Conference on Harmonization (ICH), and the ethical principles laid down in the Declaration of Helsinki. The study will be also compliance with European Directive 2001/20/EC and any applicable local regulations.

